When an appointment is made for the patient to attend the hospital clinic for initiation of 13-CRA treatment the parent(s)/legal guardian of the patient will be approached to discuss the pharmacokinetic trial and the possibility of the patient's entry into the trial; information regarding the trial may be sent to parents and patients prior to them attending. The parent(s)/legal guardian's consent to take these additional blood samples and record physiological information (local [oro-pharyngeal] tolerability, skin toxicity, adverse events) will be sought. Following parental consent, the patient will be approached and the trial procedures explained to them in order to receive their verbal and/or written assent to participate in the trial, if applicable (usually where the patient is over 7 years of age). Parents and patients may still refuse to participate in the trial at any stage prior to or during their treatment with 13-CRA. Parents and patients will be given as much time as they need to consider participation in the trial. Patients and parents may choose to share information about the research with their family or GP before they decide if they would like to take part in the trial. Investigators will ensure that families have at least 24 hours to consider involvement in the trial. In practice this is likely to be longer as parents and patients are most likely to be approached well in advance of their 13-CRA treatment period. If the parent(s)/legal guardian decide that they would not like their patient to participate in the trial then this will in no way affect the onward care of the patient.

When the patient attends hospital for initiation of 13-CRA treatment, it is anticipated that they will have a central line *in situ*. Patients will attend the clinic on Pharmacokinetic days; these will be Day 1 and Day 14 for each of the trial treatment periods. Blood samples for pharmacokinetic analysis will be taken over the course of six hours after which the patients will leave the clinic. Parents and patients will be asked if they are willing to return for an additional sample at 24-48 hours following their final dose on Day 14 of treatment.

Additional assessments will be made according to the trial procedures (section 4).

[figure not shown]
A trial schedule is presented in Appendix I.

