### 9.1 Definition of adverse events

An AE is any untoward medical occurrence in a patient or clinical trial patient administered a pharmaceutical product and which does not necessarily have a causal relationship with this treatment. An AE can therefore be any unfavourable and unintended sign (including an abnormal laboratory finding), symptom, or disease temporally associated with the use of an IMP, whether or not related to the IMP.

During the trial, any worsening of conditions, signs or symptoms noted from the time of consenting to take part in the trial will be recorded as an AE.

All AEs that occur (whether treatment related or not) will be recorded in the CRF throughout the duration of the visit (and for 14 days post dosing if recorded on the diary card or spontaneously reported to hospital staff).

As far as possible, each AE must be described by its duration (start and end time and date or ongoing), its frequency (single episode, intermittent, continuous), its severity (mild, moderate, severe - see section 9.2), a causality assessment (coexisting disease, concomitant medication, the IMP, or other cause), its relationship to the IMP (unrelated, unlikely, possibly, probably, definitely – see Section 9.2), whether this influenced the course of the IMP, whether it required specific action or therapy, and outcome.

All medical conditions present at baseline should not be considered as AEs unless these have worsened during the trial phase. In cases of surgical or diagnostic procedures the condition/illness leading to such a procedure is considered as the AE rather than the procedure itself.

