### 11.2 Safety, tolerability and palatability analyses

Reporting of the safety data will be of a descriptive nature and presented using appropriate summary statistics (e.g. n, mean, SD, %CV, median, minimum, maximum) or frequency

distributions (n%) by age group (age 1-11 years, age 12-< 21 years). Unless otherwise stated these tabulations will be supported by data listings.

Safety summaries will include all patients irrespective of whether or not they completed the trial.

AEs will be coded according to the current version of MedDRA (version to be identified in trial report).

Treatment emergent adverse events (TEAEs) will be determined and only these will be included in the statistical analysis report. Details of the criteria of classifying an AE as a TEAE will be provided in the Statistical Analysis Plan.

The incidence of adverse events will be summarised by system organ class, preferred term and maximum severity. Adverse events will also be summarised by strongest relationship to Investigational Medicinal Product by event and system organ class. If a patient experiences an adverse event more than once the event with the worst severity or at the most related to IMP occurrence will be considered. Patients will be included only once at each level where they experienced one or more events.

A summary of the incidence of serious adverse events will be presented by event and system organ class.

Adverse events relating to oro-pharyngeal tolerability data will be additionally listed separately and appropriately summarised.

All results for other safety will be appropriately summarised.

Palatability data will be appropriately summarised.

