9.2 Safety Population

The safety population is defined as all patients who receive trial medication. This population is the primary population for all safety summaries.

10 Data Reporting Conventions

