13.2 Adverse Events

AEs will be coded according to the latest version of the MedDRA dictionary. The severity of AEs will be coded according to the National Cancer Institute (NCI)-Common Terminology Criteria for Adverse Events (CTCAE) coding system version 4.03.

AEs will be deemed treatment emergent if they start on or after the time of the first dose of study medication.

All treatment emergent adverse events (TEAEs) and serious adverse events (SAEs) will be listed.

An overall adverse event summary will be presented for the categories: any TEAEs, any drug-related AEs, any Grade 3 or greater AEs, any Grade 3 or greater drug-related AEs, any TEAEs leading to death, any drug-related TEAEs leading to death, any serious TEAEs, any drug-related serious TEAEs, any TEAEs leading to discontinuations, and any drug-related TEAEs leading to discontinuations. Both number of events and number of patients will be tabulated. For patients, percentages will be calculated from the total number of patients per treatment.

Summaries of TEAEs and serious TEAEs will be tabulated by system organ class and preferred term sorted by decreasing frequency within system organ class (SOC). Both number of events and number of patients will be tabulated. For patients, percentages will be calculated from the total number of patients per treatment.

In addition, TEAEs and serious TEAEs will be summarized by maximum severity, system organ class and preferred term, and strongest relationship, system organ class and preferred term. If a patient experiences an adverse event more than once the event with the worst severity or at the most related to IMP occurrence will be considered. Patients will be included only once at each level where they experienced one or more events.

Oro-pharyngeal tolerability and symptoms will be separately assessed. Dry skin, peeling skin, cracked lips and dry eyes will be assessed by the investigator on a four point scale (0 = none, 1 = mild, 2 = moderate, and 3 = severe). Oro-pharyngeal symptoms will be assessed at baseline and following administration of 13-CRA during the Pharmacokinetic Day 14. Each symptom will be summarised by treatment and study day, presenting frequency counts and percentages for each value on the scale.

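### Three of the ten rows of the overall adverse event summary are not limited to treatment-emergent events, contrary to Protocol 11.2; in practice this exposes the Grade 3 or greater row

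*SAP*

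**What the plan says.** SAP 13.2 sets the cut-off for treatment emergence: "AEs will be deemed treatment emergent if they start on or after the time of the first dose of study medication". An event with earlier onset is therefore an AE but not a TEAE, and AE is the wider set.

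The same section lists the categories of the overall summary. The first four are "any TEAEs, any drug-related AEs, any Grade 3 or greater AEs, any Grade 3 or greater drug-related AEs". The next four are "any TEAEs leading to death, any drug-related TEAEs leading to death, any serious TEAEs, any drug-related serious TEAEs". The last two cover TEAEs, and drug-related TEAEs, that led to discontinuation. On the denominator it says: "For patients, percentages will be calculated from the total number of patients per treatment".

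The protocol is narrower. Section 11.2 says: "Treatment emergent adverse events (TEAEs) will be determined and only these will be included in the statistical analysis report". It leaves the criteria for classifying an event as a TEAE to the SAP, but not the choice of whether to restrict the report to TEAEs.

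On when recording starts, Protocol 9.1 says that "any worsening of conditions, signs or symptoms noted from the time of consenting to take part in the trial will be recorded as an AE".

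SAP section 16, where changes from the protocol are declared, mentions only the dropped summaries by age group.

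**The concern.** The SAP uses both terms within one list, so a programmer who follows it to the letter would filter seven rows on treatment emergence and leave three unfiltered. A Grade 3 event that began after consent but before any trial medication could then be counted in a table whose columns are formulations.

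The Grade 3 or greater row is the severity line in the safety overview. Protocol 1.1.1 places 13-CRA between cycles of immunotherapy, so a severe event before the first trial dose is plausible. Two faults could follow. The overview could show a Grade 3 count that the detailed TEAE tables do not support, or it could show more patients with Grade 3 events than with any TEAE. Both are avoidable inconsistencies in the trial report.

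**Working it through.** The plan states no figure to reproduce. The check compares texts, with one line of arithmetic for scale.

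**1. Count of rows (SAP 13.2).**

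| Row | Wording |
|---|---|
| Any | TEAE |
| Drug-related | AE |
| Grade 3 or greater | AE |
| Grade 3 or greater, drug-related | AE |
| Leading to death | TEAE |
| Drug-related, leading to death | TEAE |
| Serious | TEAE |
| Drug-related serious | TEAE |
| Leading to discontinuation | TEAE |
| Drug-related, leading to discontinuation | TEAE |

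Seven rows are restricted and three are not. Tables 14.3.2.2 to 14.3.2.7 are all titled as treatment emergent. Table 14.3.2.1 is not, so its title does not supply the missing restriction.

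**2. Does the analysis population remove the problem?** SAP 9.2 says: "The safety population is defined as all patients who receive trial medication". This removes patients who were never dosed. It does not remove the pre-dose events of patients who were dosed later.

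**3. Which of the three rows is exposed?** Protocol 9.3 requires a definite or plausible time sequence between administration of the investigational product and onset before an event can be rated definite, probable or possible. An event before the first trial dose should fail that test, so the two drug-related rows are largely protected. The Grade 3 or greater row has no such protection.

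**4. What the literal wording does to that row.** For one product column, let

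- A = patients with any TEAE,
- G = patients with a Grade 3 or greater TEAE (a subset of A),
- P = patients with a pre-dose Grade 3 or greater AE placed in that column and no Grade 3 or greater TEAE there.

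The literal row shows G + P; the TEAE row shows G. The overview therefore differs from the TEAE-only severity results in Table 14.3.2.3 whenever P > 0. It exceeds the any-TEAE row only if P > A − G. That is the less likely outcome, since Protocol 4.9 describes dry skin, cracked lips and dry eyes as common with 13-CRA, which would keep A − G above zero.

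**5. Scale.** SAP 7.1 hopes for 12 to 18 patients and allows up to 20. Assume that every patient receives both products, so the denominator N is the same in each column. The shift from P = 1 is 100 × 1/N percentage points:

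- N = 12: 100/12 = 8.3
- N = 18: 100/18 = 5.6
- N = 20: 100/20 = 5.0

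With the TEAE restriction the contribution is 0.

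**The case against.** **Few pre-dose events may reach the database.** Appendix I marks adverse event collection on Day 1, Day 14 and at end of trial, and leaves the pre-trial column blank. The synopsis refers to events during therapy, and Protocol section 10 to the clinic stay and 14 days after dosing. Protocol 3.2 says that "parents and patients are most likely to be approached well in advance of their 13-CRA treatment period", but that concerns when families are approached. It gives no consent date, and the gap from consent to first dose is stated nowhere. This stands as a limit on how often the problem arises. It does not cancel the rule in Protocol 9.1, which starts at consent.

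**Two of the three rows protect themselves through causality.** This largely stands. Patients already taking 13-CRA are eligible (Protocol 6.1), which leaves some room for a pre-dose event to be rated as related. However, Protocol section 7 defines the investigational product as the trial liquid, so earlier capsule cycles fall outside it.

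**It is probably a drafting slip, and correct severity data appear anyway in Tables 14.3.2.3 and 14.3.2.6.** That is likely, and it lowers the stakes. It is also a reason to correct the text.

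**A reader might infer that the wording biases the safety comparison against one formulation, or against whatever is given in Month 1.** The documents do not support that. The SAP has no rule for assigning a pre-dose event to a product, and a by-treatment program might simply omit it. If such events were placed under the Month 1 product, the order is randomised, so neither formulation would be favoured in expectation.

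**Conclusion.** The contradiction is real: three of ten categories in SAP 13.2 are wider than Protocol 11.2 allows, and the change is undeclared. Its practical reach is essentially one descriptive row, Grade 3 or greater. One affected patient would shift that row by 5.0 to 8.3 percentage points. This assumes 12 to 20 patients who all receive both products, that the event is recorded, that it is placed in a product column, and that the patient has no Grade 3 or greater TEAE under that product. The documents establish neither the recording nor the placement.

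A reader should not conclude that all three rows will be inflated, or that any formal inference is affected: Protocol 11.3.3 has safety data simply summarised, with no hypothesis test. The point is minor but clear, and worth correcting because the correction costs almost nothing.

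**What to change.** In SAP 13.2, reword the three categories as drug-related TEAEs, Grade 3 or greater TEAEs, and Grade 3 or greater drug-related TEAEs. Apply the treatment-emergent filter to all ten rows of Table 14.3.2.1.

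State that any AE with onset before the first dose appears only in Listing 16.2.7.1, flagged as pre-treatment. This also means amending the sentence in 13.2 on listings, which at present commits only to TEAEs and SAEs and so does not cover a non-serious pre-dose event.

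If the wider set is intended for these rows, declare it in SAP section 16 and show pre-dose events separately from the two product columns.

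The cost is three changed words, one amended sentence, one filter in the table program and a flag in one listing. No new data are needed.

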## 5.2 Criteria Prior to starting each cycle of 13-CRA

1. Total bilirubin  $\leq 1.5$  x normal, and (SGPT) ALT  $\leq 5$  x normal. Veno-occlusive disease if present, should be stable or improving.
2. Skin toxicity no greater than CTCAE Grade 1
3. Serum triglycerides  $< 5.65$  mmol/L.
4. No haematuria and / or proteinuria on urinalysis.
5. Serum calcium  $\geq 2.0$  mmol/L to  $\leq 2.9$  mmol/L.
6. Serum creatinine based on age / gender as follows:

Age	Maximum Serum Creatinine $\mu$ mol/L	
	Male	Female
1 month to $< 6$ months	35	35
6 months to $< 1$ year	44	44
1 to $< 2$ years	53	53
2 to $< 6$ years	70	70
6 to $< 10$ years	88	88
10 to $< 13$ years	106	106
13 to $< 16$ years	132	124
$\geq 16$ years	150	124

7. Patients with a seizure disorder must be well controlled and taking anticonvulsants. CNS toxicity  $<$  grade 2 (CTCAE).

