# 6 TREATMENT OF PATIENTS

## 6.1 Evaluation of test and reference treatment

Evaluation of the test and reference product will occur during two months of the therapy only.

Consent to take part in the trial will be obtained before any trial procedures are undertaken.

Patients who are already receiving 13-CRA treatment will also be eligible for the trial, so long as they are able to commit to two cycles of trial 13-CRA. The next planned 14-day treatment cycle will be classed as My-CRA Month 1. After consent to take part has been obtained and prior to the initiation of the next 14 day treatment patients will be randomised to receive either 13-CRA liquid (test product) or liquid extracted from capsule (reference product) in My-CRA Month 1. Randomisation will be done once eligibility has been confirmed and their next scheduled treatment visit is booked, in order that the appropriate medication can be made available for the

patient's visit. Randomisation will be done centrally by Nova according to a randomisation list generated by the trial statistician, investigators will email (or telephone) Nova to receive randomisation details, this will be confirmed by email as "liquid first" or "extracted capsules first", pharmacy contacts will also be notified. After My-CRA month 1, patients will then cross over to the alternative formulation in My-CRA Month 2. In all other treatment cycles patients will revert to standard therapy i.e. liquid extracted from capsules. The pharmacokinetics of 13-CRA will be evaluated during test and reference treatments (My-CRA Month 1 and 2).

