**APPENDIX I TRIAL SCHEDULE: EACH CYCLE**

Test	Pre trial	Day 1	Day 14	Day 15/16	End of trial  (Day 29)
Informed consent / assent 	x				
Medical history	x				
Concomitant medications	x	x	x		x
Physical Examination	x				
Pregnancy Test 	x				
Check for central line in situ	x	x			
13-CRA morning dose		x	x		
Pharmacokinetic blood samples 		x	x	x	
Vital signs for safety 		x	x		
Palatability 			x		
Oro-pharyngeal tolerability 		x	x		x
Adverse events / serious adverse events 		x	x		x

- 1 Parents/legal guardian will be asked to give informed consent to their child participating in the pharmacokinetic trial before 13-CRA is administered. Patients over the age of 7 years will be asked to give their assent to participate in the pharmacokinetic trial if it is deemed appropriate.
- 2 Pregnancy test for females of childbearing age, not more than 7 days prior to starting treatment (each cycle).
- 3 Up to five pharmacokinetic blood samples will be taken.
- 4 Systolic and diastolic blood pressure, pulse and body temperature at baseline (in older patients this will be following 5 mins rest in supine position).
- 5 Palatability assessment will be made at the 14 day visit. This will be done using a face to face survey.
- 6 Assessed at baseline and during the trial and follow up
- 7 On discharge from site or withdrawal from trial (AEs followed for up to 14 days later, if in diary card or if reported to research staff.

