13.4 Vital Signs

Vital signs will be collected at Day 1 and Day 14 of each treatment. Baseline vital signs will be determined as those at Day 1 for each treatment.

The result and change from baseline of each treatment in vital signs parameters (systolic and diastolic blood pressure, pulse and temperature) will be listed and summarized descriptively for each scheduled time-point during the study.

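### SAP 13.2 sets no per-cycle baseline and plans no shift summary for the 0–3 symptom scores, so Table 14.3.2.8 will not show how many patients worsened within a cycle on each formulation

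*SAP*

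**What the plan says.** SAP 13.2 describes the scale: "Dry skin, peeling skin, cracked lips and dry eyes will be assessed by the investigator on a four point scale". On timing it says: "Oro-pharyngeal symptoms will be assessed at baseline and following administration of 13-CRA during the Pharmacokinetic Day 14". It does not say that baseline means Day 1 of each cycle. The planned output is: "Each symptom will be summarised by treatment and study day, presenting frequency counts and percentages for each value on the scale". Table 14.3.2.8 is the only table for these scores, and Listing 16.2.7.3 is the matching patient listing.

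Vital signs are treated differently in SAP 13.4: "Baseline vital signs will be determined as those at Day 1 for each treatment". Change from that baseline is then summarised.

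The protocol schedule is headed "APPENDIX I TRIAL SCHEDULE: EACH CYCLE". Its oro-pharyngeal tolerability row is marked at Day 1, Day 14 and end of trial, with the footnote "Assessed at baseline and during the trial and follow up". Protocol 3.5 adds that this assessment is made both before and after dosing.

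Three provisions bear on the score a patient may have when a cycle starts:
- Protocol 6.1: "Patients who are already receiving 13-CRA treatment will also be eligible for the trial".
- Protocol 5.2, criteria for starting each cycle: "Skin toxicity no greater than CTCAE Grade 1".
- Protocol 1.1.3 and SAP section 3: the second cycle starts 14 days after the first ends, with up to 7 more days allowed.

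**The concern.** Protocol 4.9 names these symptoms as common effects of 13-CRA, and skin toxicity and oro-pharyngeal tolerability are listed secondary endpoints. The useful safety question for a formulation comparison is how many patients got worse during a cycle on the liquid, and how many on the extracted capsule.

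A Day 14 score of 1 can be new in that cycle or unchanged from Day 1. Separate frequency columns for Day 1 and Day 14 do not link the two scores of one patient, so they do not distinguish these cases. In Month 2 the Day 14 column for one formulation may also include symptoms that began on the other.

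At stake is the readability of a named secondary safety endpoint. No decision rule or primary result depends on it.

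**Working it through.** The documents give no figure on this point, so there is nothing to reproduce. The check asks what the two planned columns can reveal about within-cycle worsening.

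**Inputs from the documents.** The scale runs from 0 to 3, there are two treatments and four symptoms, and at most 20 patients (SAP 7.1). The break between cycles is 14 to 14 + 7 = 21 days.

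**Inputs assumed.** All score counts below are illustrative.

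**Two-level case (scores 0 and 1 only).** Let *a* and *b* be the numbers scoring 1 on Day 1 and Day 14, *w* the number who worsened and *r* the number who recovered. Then b = a + w − r, so w = (b − a) + r. The columns fix the net shift b − a but not r. Since w cannot exceed the number who started at 0 (N − a) or the number who end at 1 (b):

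max(0, b − a) ≤ w ≤ min(N − a, b)

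With N = 20:
- a = 8, b = 8: from max(0, 0) = 0 to min(12, 8) = 8, that is 0% to 40%.
- a = 4, b = 8: from 4 to min(16, 8) = 8, that is 20% to 40%.
- a = 0, b = 8: from 8 to min(20, 8) = 8, so exactly 8.

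**A case with moderate scores.** Day 1 counts for scores 0/1/2/3 are 12/8/0/0 and Day 14 counts are 8/8/4/0.
- Minimum: patients scoring above 0 rise from 8 to 12, so at least 4 worsened. This is reached if four patients go from 0 to 2 and everyone else is unchanged.
- Maximum: only the 12 patients above 0 on Day 14 can have worsened. This is reached if all 12 who started at 0 move up and all 8 who started at 1 return to 0.
- Range: 4 to 12 of 20, that is 20% to 60%. A linear-programming search over all possible cross-tables gave the same bounds, here and in the three cases above.

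The columns are fully informative when every Day 1 score is 0. The three provisions on cycle start do not ensure that.

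**Other planned outputs.**
- *Listing 16.2.7.3* would give the answer, but only by pairing up to 4 × 2 × 20 = 160 Day 1 and Day 14 scores by hand, with no stated baseline rule.
- *Adverse event tables* do not give it. Under Protocol 4.10 only local changes judged clinically relevant become adverse events. Protocol 9.1 judges worsening from consent or over the trial phase. SAP 13.2 counts treatment emergence from the first dose of study medication, and this does not reset at Month 2.

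**The case against.** A reader might infer that symptoms carried in from earlier 13-CRA cannot be separated at all from those of the cycle, or that the skin endpoint would say nothing about each formulation. The documents do not support either reading. The table is split by day, so any Day 1 frequencies collected sit beside those of Day 14. The listing gives every patient's scores, sorted by sequence, patient and treatment. Worsening can also be recorded as an adverse event with its severity. All of that stands, and it limits the point to what is summarised, not what is knowable.

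Further objections:
- *The 40% is an extreme.* It needs all 8 symptomatic patients to recover during 14 days on the drug while 8 others become symptomatic. That is fair: the range shows what the columns allow, not what is likely.
- *High starting scores should be uncommon*, because skin toxicity above Grade 1 bars the start of a cycle. This is also fair, although the CTCAE grade and the 0–3 scale are different scales and the criterion still allows a score above zero.
- *Randomised order means symptoms carried in from before the trial do not systematically favour either formulation.* This stands for the comparison of treatments. It does not supply the number who worsened.
- *A within-cycle shift does not remove carry-over.* The Month 2 Day 1 score may itself contain residual effects of the first formulation, so the shift mixes their resolution with new onset. This stands and shapes the fix.
- *Frequencies by visit satisfy a promise of descriptive reporting, and vital signs are continuous.* Frequencies are acceptable as far as they go. A shift table is also descriptive and is the ordinal counterpart of change from baseline.
- *It is not certain that a Day 1 score exists in each cycle.* The Appendix I row does not name the four symptoms, and the each-cycle schedule also holds one-off items such as consent. This stands and needs checking.

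**Conclusion.** The point holds as a gap in the planned summary. SAP 13.2 gives these scores no per-cycle baseline and no shift or change summary, so Table 14.3.2.8 shows net movement between days and in general not how many patients worsened on each formulation. No other planned table fills the gap. A reader would have to work it out from the listing.

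The size cannot be stated from the documents. Under assumed counts the uncertainty runs from none (all Day 1 scores zero) to 0–8 of 20 or 4–12 of 20. The conclusion rests on some patients starting a cycle with a score above zero, which the plan permits but does not quantify.

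This is a worthwhile, low-cost improvement to a descriptive secondary safety output. It does not touch the pharmacokinetic analysis.

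**What to change.** In SAP 13.2:
1. Define baseline for each symptom as the pre-dose Day 1 score of the same treatment cycle, in line with SAP 13.4.
2. Add to Table 14.3.2.8 a Day 1 to Day 14 shift table for each symptom and treatment, with the number and percentage of patients whose score rises by at least 1 point. Keep the raw frequencies beside it.
3. Show the shift by period or sequence as well, and note that Month 2 baselines may include residual effects of the first formulation.
4. Confirm against the CRF that all four symptoms are scored before dosing on Day 1 of both cycles. If some are not, state which cycles can be included.

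The cost is a few sentences of SAP text and one extended table. If the CRF check succeeds, no extra visit, assessment or data item is needed.
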